Show the Kaplan-Meier survival curve until the onset of event in the “full analysis set” and calculate the point estimation value of survival rate and its 95% confidence intervals (two-sided) at the quantile of PFS and specified time points. The Log-Log conversion of Brookmeyer and Crowley²³⁾ will be used to calculate the 95% confidence intervals of the quartiles for PFS.

- Overall survival (OS)

OS is the period from the day of enrollment until death by all causes. For surviving subjects, the period is terminated on the final day of confirming survival or data cut-off date, whichever occurs earlier.

[Analysis method]

The analysis will be performed in the same manner as for PFS in the “full analysis set”.

- Response rate (RR)

RR is the percentage of subjects whose best overall response after enrollment according to RECIST ver 1.1 (see Appendix A) is either CR or PR. Overall response will be graded by favorability in the order of CR, PR, SD, PD, and NE. Best overall response is the best response recorded in the throughout of all courses.

[Analysis method]

RR of target lesion and its 95% confidence interval (two-sided) will be calculated in the “full analysis set”.

- Duration of response (DOR)

DOR is the period from the day when either CR or PR is first confirmed until the day of documented progression or the day of death due to all causes, whichever occurs earlier. For surviving subjects without documented progression, the period will be cut off on the final day when specified diagnostic imaging reveals no PD (final day of confirming progression-free survival). For surviving subjects without documented progression for whom curative resection is indicated during protocol treatment, the period will be cut off on the final day when specified preoperative diagnostic imaging reveals no PD (final day of confirming progression-free survival).

[Analysis method]

Show the Kaplan-Meier survival curve until the onset of event for the subjects who showed response among the “full analysis set” and calculate the point estimation value of survival rate and its 95% confidence interval (two-sided) at the quantile of survival period and specified time points.

- Disease control rate (DCR)

DCR is the percentage of subjects whose best overall response after enrollment according to RECIST ver 1.1 (see Appendix A) is CR, PR, or SD. Overall response will be graded by favorability in the order of CR, PR, SD, PD, and NE

[Analysis method]

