7.2.4 Efficacy analysis

7.2.4.1 Primary endpoint and analysis method

[Primary endpoint]

Progression-free survival (PFS rate) at 6 months after enrollment

The PFS rate 6 months after enrollment, the primary endpoint, is the gross proportion of surviving subjects without documented progression up to 6 months after enrollment (date of enrollment + 24 weeks \pm 2 weeks), counting from the day of enrollment. Subjects with no imaging data on progression at 6 months after enrollment and subjects lost to follow-up will be included in the denominator, but will not be handled as progression-free.

Definition of progression:

Progression will include both progressive disease (PD) based on diagnostic imaging assessed according to RECIST ver. 1.1 and primary disease progression that cannot be confirmed by diagnostic imaging (clinical progression). When progression is documented by diagnostic imaging, the day on which the diagnostic imaging is performed will be the progression date. For clinical progression, the day of the clinical determination will be the progression date. In a case in which, for example, tumor diameter has become extremely small, if the status is determined to be “not definite progression” clinically, although the assessment is PD according to the response criteria, the assessment of PD according to the response criteria will take precedence and the status will be considered progression. (In this case, the clinical determination on continuing protocol treatment will take precedence.) Even if the assessment is not PD according to the response criteria, if there is

definite clinically documented progression, the clinical determination will take precedence and the status will be considered progression. For surviving subjects without documented progression, the period will be cut off on the final day when a progression-free status is confirmed (final day of progression-free survival confirmation). Confirmation of progression-free status by imaging test or sample test is not mandatory, and clinical confirmation by outpatient medical examination, etc., will be allowed. Contact by telephone only will not be allowed. Events and the cut-off will also be handled the same way in subjects who have discontinued protocol treatment for reasons such as toxicity and refusal of treatment, even if another (follow-up) therapy is added. Thus, the time of treatment discontinuation or the day of follow-up treatment initiation will not be the cut-off.

[Main analysis]

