7.2.4.2 Secondary endpoints and analysis method

[Secondary endpoints]

1) Progression-free survival (PFS)

PFS is the period from the day of enrollment until the day of documented PD (radiological decision or clinical decision) or the day of death due to any cause, whichever comes earlier.

For surviving subjects without documented progression, the period will be cut off on the final day on which progression-free status is confirmed (final day of progression-free survival confirmation). Events and the cut-off will also be handled the same way in subjects who have discontinued protocol treatment for reasons such as toxicity and refusal of treatment, even if another (follow-up) therapy is added. Thus, the time of treatment discontinuation or the day of follow-up treatment initiation will not be the cut-off.

[Analysis method]

Kaplan-Meier method will be used to illustrate survival curve until the onset of event in the “full analysis set,” and the point estimation value of survival rate and its 95% confidence interval (two-sided) will be calculated at the quartile of PFS and specified time points. The

Log-Log conversion of Brookmeyer and Crowley will be used to calculate the 95% confidence intervals of the quartiles for PFS.

2) Overall survival (OS)

OS is the period from the day of enrollment until death by any cause. For surviving subjects, the period is terminated on the final day of survival confirmation or data cut-off date, whichever occurs earlier.

[Analysis method]

Kaplan-Meier method will be used to illustrate survival curve until the onset of event in the “full analysis set,” and the point estimation value of survival rate and its 95% confidence interval (two-sided) will be calculated at the quartile of OS and specified time points. The Log-Log conversion of Brookmeyer and Crowley will be used to calculate the 95% confidence intervals of the quartiles for OS.

3) Response rate (RR)

RR is the percentage of subjects whose best overall response after enrollment according to RECIST ver. 1.1 is either complete response or partial response. Overall response will be graded by favorability in the order of complete response (CR), partial response (PR), stable disease (SD), progressive disease (PD), and not evaluable (NE). Best overall response is the best response recorded throughout all courses.

[Analysis method]

RR of target lesion and its 95% confidence interval (two-sided) will be calculated in the “full analysis set.”

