Further, the maximum tumor reduction rate will be calculated for each subject, and a waterfall plot will be created by arranging the maximum tumor reduction rate in ascending order. Lines of reference at -30% indicating PR and at + 20% indicating PD will be drawn.

$$\text{Reduction ratio of SoD} = \frac{\text{SoD at evaluation point} - \text{SoD before treatment}}{\text{SoD before treatment}} \times 100\%$$

4) Duration of response (DOR)

DOOR is the period from the day when either CR or PR is first confirmed until the day of documented PD or the day of death due to any cause, whichever occurs earlier. For surviving subjects without documented PD, the period will be cut off on the final day of progression-free survival confirmation.

[Analysis method]

The Kaplan-Meier survival curve will show the subject status until the onset of event for the subjects who showed response among the “full analysis set,” and the point estimation value of survival rate and its 95% confidence interval (two-sided) will be calculated at the quartile of DOOR and specified time points.

5) Disease control rate (DCR)

DCR is the percentage of subjects whose best overall response after enrollment according to RECIST ver. 1.1 is CR, PR, or SD.

[Analysis method]

DCR and its 95% confidence interval (two-sided) will be calculated in the “full analysis set.”

6) Time to treatment failure (TTF)

TTF is the period from the day of enrollment until the day of the decision to discontinue protocol treatment, the day of documented progression during protocol treatment (day of decision on clinical PD or radiological PD), or the day of death due to any cause, whichever comes earlier. Subjects not included in the above criteria will be censored at the dose starting date in the final course.

[Analysis method]

Kaplan-Meier method will be used to illustrate survival curve until the onset of event in the “full analysis set,” and the point estimation value of survival rate and its 95% confidence interval (two-sided) will be calculated at the quartile of TTF and specified time points. The Log-Log conversion of Brookmeyer and Crowley will be used to calculate the 95% confidence intervals of the quartiles for TTF.

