7.2.7.12 List of determinations of PD

Display items:

Subject No., enrollment phase, DLT evaluation set, full analysis set, safety analysis set, sex, age (years), start date of protocol treatment, day of decision on clinical PD, day of decision on radiological PD, final day of imaging test, final day on which progression-free survival is confirmed, start date of follow-up treatment

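### The SAP's censoring rule for duration of response departs from the protocol: it drops the imaging condition and the curative-resection rule, and its revision log gives no reason.

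*SAP*

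**What the plan says.** **Protocol 13.3.3.2 (DOR).** For surviving responders without documented progression, "the period will be cut off on the final day when specified diagnostic imaging reveals no PD". A second rule covers responders "for whom curative resection is indicated during protocol treatment": they are censored at the last specified preoperative scan without PD. Both protocol texts in the file carry both rules.

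**SAP 7.2.4.2 4), version 4.0.** For the same subjects, "the period will be cut off on the final day of progression-free survival confirmation". Imaging and resection are not mentioned. Version 3.0 reads the same way; versions 1.0 and 2.0 contain both protocol rules.

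**What the SAP date means.** SAP 7.2.4.1 states that a scan is not required to confirm progression-free status and that "clinical confirmation by outpatient medical examination, etc., will be allowed". Listing 7.2.7.12 shows two separate items: "final day of imaging test, final day on which progression-free survival is confirmed".

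**Revision log (SAP section 1).** Version 3.0 cites items linked to protocol revision 2.0, completion of administration, and dose reduction. Version 4.0 lists several sections, but not 7.2.4.2.

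**The concern.** The two governing documents define the censoring date of a named secondary endpoint differently, so the same data can give two DOR results. Whoever programs from the SAP would naturally take the progression-free-confirmation date, because the listing holds it apart from the last imaging date. Protocol 9.2.10 adds that when follow-up is lost, the last visit is recorded as that confirmation date. Time after the last scan can then count as continuing response. A responder who goes to surgery has no stated handling at all.

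Protocol 13.1 leaves detailed endpoint definitions to the SAP, but here the SAP removes a rule the protocol states explicitly. The protocol revision cited for version 3.0 does not explain this, since both protocol texts keep the rules. The sensitivity analyses in SAP 7.4 cover only the 6-month PFS rate and PFS, so nothing planned would show the difference for DOR.

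**Working it through.** The documents give no expected DOR, number of responders or precision target, so there is no planned figure to reproduce.

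**1. Direction of the censoring-date change.** The Kaplan-Meier estimate is S(t) = ∏(1 − d_j/n_j) over event times up to t. The events are the same under both rules. The protocol counts follow-up "until the day of documented progression or the day of death due to all causes, whichever occurs earlier", and progression includes clinical progression; the SAP's PFS paragraph likewise counts a radiological or a clinical decision as PD. Moving a censoring time later leaves every d_j unchanged and can only raise n_j or leave it unchanged. The SAP curve is therefore equal to or above the protocol curve.

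**2. Size, by simulation (3,000 runs per setting).**

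- From the documents: scans every 56 days with a ±7-day window (protocol 9.2.10, Table 9.c), and 14-day visits while on treatment.
- Assumed: 8 or 20 responders; exponential DOR with true median 120 or 200 days; data cut-off uniform between 180 and 720 days after response; 0 or 25% of progressions found clinically; 0 or 20% of responders leaving imaging but still seen every 14 days until cut-off. As a guide to the smaller number, the 13.5% response rate quoted in protocol 4.1.3.3 for panitumumab alone gives 0.135 × 52 ≈ 7.

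Mean S(252 days), protocol rule → SAP date:

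| Responders, true median | Scans exactly on schedule | ±7 days | ±7 days, 25% clinical PD | As previous, 20% leave imaging |
|---|---|---|---|---|
| 8, 120 d | 0.278 → 0.278 | 0.266 → 0.273 | 0.263 → 0.269 | 0.252 → 0.306 |
| 8, 200 d | 0.459 → 0.459 | 0.451 → 0.459 | 0.439 → 0.447 | 0.426 → 0.474 |
| 20, 120 d | 0.274 → 0.274 | 0.267 → 0.275 | 0.259 → 0.267 | 0.250 → 0.302 |
| 20, 200 d | 0.461 → 0.461 | 0.450 → 0.458 | 0.437 → 0.445 | 0.433 → 0.480 |

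By column the differences are 0, 0.007–0.008, 0.006–0.008 and 0.047–0.054. The first is zero because every event falls on a common scan day, and moving a censoring date to a visit before the next scan crosses no event time. The typical median was unchanged or 1 to 14 days longer (the largest change was 126 to 140 days). The SAP curve was never the lower one at 112, 168 or 252 days in any of the 16 settings.

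A separate simulation with 19 responders, read at 6 months, gave 49.9% against 54.6% (4.7 points) when 20% stopped scans and had 180 further days of clinic follow-up. At 30% it gave 49.7% against 56.5% (6.8 points). The assumed share leaving imaging sets the upper end.

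**3. Resection rule.** Take seven responders: events at 56, 112, 112, 168, 224 and 280 days, and one subject resected after a clear scan at day 112. Under every rule S(112) = 6/7 × 4/6 = 0.571.

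- Protocol, censored at 112: S(168) = 0.571 × 2/3 = 0.381; median 168 days.
- SAP, no relapse, censored at 336: S(168) = 0.571 × 3/4 = 0.429; median 168 days.
- SAP, relapse at 140: S(168) = 0.571 × 3/4 × 2/3 = 0.286; median 140 days.

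Dropping the rule can therefore raise or lower the estimate.

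**The case against.** The SAP's DOR sentence does not say that the confirmation is clinical. The protocol puts a near-identical label in brackets after the imaging date, so the sentence could be shorthand for that date. This stands as an ambiguity. However, 7.2.4.1 and listing 7.2.7.12 make the no-scan reading the natural one, and the SAP should not leave it open.

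A reader might infer that DOR computed from the SAP is biased upward, or always longer. The documents do not support that. The comparison is between two censoring rules, not with true DOR. Clinical progression and death count as events, so time up to a clinic visit is not empty follow-up. In the simulations both rules lay above the assumed true curve at 252 days, because scans detect progression late. The resection component has no fixed direction.

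Loss of imaging may also be uncommon. Follow-up scans are marked as needed in the study calendar, but protocol 9.2.10 asks for a scan within 28 days when withdrawal is not for imaging PD, and collects later radiological PD and last-scan dates. If no censored responder has a confirmation date after the last scan and none is resected, the two results coincide.

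Finally, DOR is descriptive, and its sampling error is large: with 20 responders at 50%, √(0.25/20) = 0.11. That limits the consequence, but it does not justify conflicting definitions.

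**Conclusion.** The discrepancy is real and can be seen in the two texts. It entered at SAP version 3.0 with no logged reason. For the same events, the SAP date gives a DOR curve equal to or higher than the protocol's imaging date: about 0 to 5 points at 252 days in the main simulations. Values near 5 need an assumed 20% of responders followed only in clinic. The number of responders, the true median and the cut-off pattern are also assumptions, so the actual size is unknown. Omitting the resection rule can move the estimate in either direction, and the documents give no expected frequency of resection.

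Version 3.0 is dated December 2017, after the planned end of enrollment in March 2017, in an open-label study. A reader might infer that the change was prompted by results; nothing in the documents shows that. The primary test is unaffected. This is a correction that should be made to a reported secondary endpoint, not a threat to the trial's main conclusion.

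**What to change.** In SAP 7.2.4.2 4), restore the protocol's two rules as SAP version 2.0 had them: censor at the last specified scan without PD, and at the last specified preoperative scan without PD when curative resection is indicated. If the sponsor wants the progression-free-confirmation date, report it as a labelled sensitivity analysis and log the reason.

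The cost is a sentence or two in the SAP and one revision-log entry. Scan and confirmation dates are already collected (protocol 9.2.10) and listed (SAP 7.2.7.12). One practical point: protocol 8.7 and 9.2.11 name no field for on-study surgery, so resected responders may have to be identified from the details recorded under other reasons for discontinuation.

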7.2.4.3 Subgroup analysis of efficacy

1) Subgroup analysis on the following items will be performed for each background factor described below. The same analysis method will be used as in Sections 7.2.4.1 and 7.2.4.2. Using all background factors as explanatory variables, multivariate analysis will be performed using the Cox proportional hazard model for PFS, OS, and TIF. Similarly, using all background factors as explanatory variables, logistic regression analysis will be performed for PFS rate and DCR.

7.2.4.3.1.1 PFS rate

7.2.4.3.1.2 PFS

7.2.4.3.1.3 OS

7.2.4.3.1.4 RR

7.2.4.3.1.5 DCR

7.2.4.3.1.6 TTF

Background factors:

Age (≥ 20 years < 65 years, ≥ 65 years < 75 years), sex, ECOG Performance status (P.S.) [before dosing on Day 1 of Course 1 (0, 1)], information on primary tumor location [right, left], adjuvant chemotherapy (yes, no), resection of primary lesion (yes, no), number of days since the start of first-line treatment (< 600 days, ≥ 600 days)

2) A landmark analysis for PFS, OS, and TIF will be performed for each landmark point after enrollment. Patients developing applicable events by the landmark point after enrollment and those who have been discontinued will be excluded from the analysis. The same analysis method will be used as in Section 7.2.4.2.

7.2.4.3.2.1 PFS

7.2.4.3.2.2 OS

7.2.4.3.2.3 TTF

Factor	Landmark point	Category
Skin Toxicity,	Week 6	$\leq G1, \geq G2$
Skin Toxicityr	Week 10	$\leq G1, \geq G2$

Factor	Landmark point	Category
Stomatitis	Week 6	$\leq G1, \geq G2$
Stomatitis	Week 10	$\leq G1, \geq G2$
Neutropenia	Week 6	$\leq G0, \geq G1$
Neutropenia	Week 6	$\leq G2, \geq G3$
Early Tumor Shrinkage (ETS)*	Week 8	Yes, No

*ETS refers to the case of tumor shrinkage by at least 20% within 8 weeks after enrollment.

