On the other hand, for TAS-102, in the domestic phase II study in previously treated subjects with unresectable, advanced/recurrent colorectal cancer refractory or intolerant to fluoropyrimidine agents, OXA, and IRI and has treatment history of 2 regimens of standard chemotherapy, the secondary endpoint PFS median assessed by the Investigator were 1.0 months in the placebo group but significantly prolonged to 2.7 months in the TAS-102 group (HR = 0.35, two-sided 95% CI 0.25 to 0.50, $p < 0.0001$).

As increased anti-tumor effect can be expected by using TAS-102 in combination with panitumumab treatment which is the standard treatment for patients with unresectable, advanced/recurrent colorectal cancer, the PFS rate at 6 months in this study was assumed to be 48% and this was set as the expected

value for the panitumumab treatment in combination with TAS-102 therapy in patients with RAS wild-type unresectable, advanced/recurrent colorectal cancer. *Also, for the threshold where* further testing for panitumumab treatment in combination with TAS-102 may be considered not necessary, it was assumed to be 29% from the CI lower limit of the PFS rate at 6 months in the ASPECCT study.

For the main analysis, based on the observed PFS rate at 6 months from start of treatment, binomial test will be conducted on the null hypothesis “the true PFS rate at 6 months from start of treatment will be not more than the PFS threshold rate where value is determined invalid”. With the PFS threshold rate at 29%, PFS expected rate at 48% at 6 months from start of treatment, and one-sided significant level at 5.0%, power at 80%, the necessary number of subjects will be 47. Taking into consideration of ineligible or discontinued subjects at approximately 10%, the target number of subjects was set to 52 (including subjects that received RD in the phase I part).

Study period:

Total study period: November 2015 to March 2018 (29 months)

Enrollment period: November 2015 to March 2017 (17 months)

Follow-up period: 12 months after completion of enrollment

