As increased anti-tumor effect can be expected by using TAS-102 in combination with panitumumab treatment which is the standard treatment for patients with unresectable, advanced/recurrent colorectal cancer, the PFS rate at 6 months in this study was assumed to be 48% and this was set as the expected value for the panitumumab treatment in combination with TAS-102 therapy in patients with RAS wild-type unresectable, advanced/recurrent colorectal cancer. *Also, for the threshold where* further development for panitumumab treatment in combination with TAS-102 may be considered not necessary, it was assumed to be 29% from the CI lower limit of the PFS rate at 6 months in the ASPECCT study.¹⁷⁾

For the main analysis, based on the observed PFS rate at 6 months from start of treatment, binomial test will be conducted on the null hypothesis “the true PFS rate at 6 months from start of treatment will be not more than the PFS threshold rate where value is determined invalid”. With the PFS threshold rate at 29%, PFS expected rate at 48% at 6 months from start of treatment, and one-sided significant level at 5%, power at 80%, the necessary number of subjects will be 47. Taking into consideration of ineligible or discontinued subjects at approximately 10%, the target number of subjects was set to 52 (including subjects that received RD in the phase I part).

6.3 Discontinuation of entire clinical study or discontinuation of clinical study at a study site

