
The following analysis will be performed on the “full analysis set.”

PFS rate at 6 months is calculated by counting of subjects with progression, without progression, and unconfirmed at 6 months. Based on the observed PFS rate at 6 months from the day of enrollment, binomial test will be conducted on the null hypothesis “value will be determined invalid at PFS rate $\leq 29\%$.” Significant level will be 2.5% (one-sided) in the main analysis. For interval estimation, accurate 90% confidence interval (two-sided) based on binomial distribution will be used.

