7.2.4.5 Level of significance, confidence coefficient

Significance level: Main analysis only, 5% (one-sided); other analyses, 5% (two-sided)

Confidence coefficient: Main analysis only, 90% (two-sided); other analyses, 95% (two-sided)

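### SAP v4.0 repeats the binomial test against 29% in 14 subgroups without multiplicity control; 12 of the 14 first appear in a version dated just over three months after the planned study end

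*SAP*

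**What the plan says.** SAP v4.0 section 7.2.4.3 lists six endpoints for subgroup analysis, with the PFS rate first. The seven factors are age (cut at 65), sex, performance status, tumor side, adjuvant chemotherapy, primary resection, and time since first-line treatment began (cut at 600 days). On method it says: "The same analysis method will be used as in Sections 7.2.4.1 and 7.2.4.2".

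For the PFS rate, the method in section 7.2.4.1 is a count, a test ("binomial test will be conducted on the null hypothesis" that the rate is at most 29%) at one-sided 2.5%, and an exact 90% confidence interval. Section 7.2.4.5 sets the levels: "Main analysis only, 5% (one-sided); other analyses, 5% (two-sided". Section 7.2.4.3 contains no multiplicity rule, does not call its results exploratory, and does not exempt subgroups from the test.

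The protocol's efficacy analysis and SAP v2.0 contain no subgroup analysis. SAP v3.0 (28 December 2017) has tumor side only. The other six factors, the landmark analyses and the multivariable models appear in v4.0 (10 July 2018). The protocol summary gives "Total study period: November 2015 to March 2018 (29 months" as the planned period.

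**The concern.** Read literally, the plan tests the same null 14 times on overlapping data and controls the error rate of none of them jointly. A missed primary test could then be followed by a subgroup reported as significant.

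The null also does not suit a subgroup. Protocol section 6.2.2.2 takes the 29% from the lower confidence limit of the 6-month PFS rate in the whole panitumumab arm of a monotherapy trial, where the estimate was 33% (95% CI 29% to 37%). In a single-arm trial, a subgroup with better prognosis can exceed 29% even if TAS-102 adds nothing. This problem would remain if only one subgroup were tested.

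The timing adds to it. Twelve of the 14 subgroups entered the plan late in an open-label trial, and no reason is given for the 600-day cut.

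**Working it through.** **1. The plan's own figure.** Inputs from protocol section 6.2.2.2: "With the PFS threshold rate at 29%, PFS expected rate at 48% at 6 months from start of treatment", "one-sided significant level at 5%, power at 80"%, N = 47. With X ~ Binomial(47, p), the rule is X ≥ 20:
- P(X ≥ 20 | p = 0.29) = 0.0327, below 0.05
- P(X ≥ 20 | p = 0.48) = 0.814, above 0.80

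So 47 is reproduced. Adding 10% gives 47 × 1.1 = 51.7, or the stated target of 52. This is the only test that the trial was sized for.

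**2. Number of subgroup tests.** 7 factors × 2 levels = 14. New in v4.0: 6 × 2 = 12.

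**3. Level.** Section 7.2.4.1 gives one-sided 2.5%. Section 7.2.4.5 gives two-sided 5% to non-main analyses, which is 2.5% in the upper tail. Both routes give subgroups 2.5%. One-sided 5% is reserved for the main analysis. (Sections 7.2.4.1 and 7.2.4.5 disagree on the level of the main analysis itself; that is a separate matter.)

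**4. Single tests at 2.5%.** The critical value is the smallest k with P(X ≥ k | m, 0.29) ≤ 0.025.

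| m | k | P(reject), true 29% | P(reject), true 33% |
|---|---|---|---|
| 52 (overall) | 23 | 0.014 | 0.060 |
| 36 | 17 | 0.016 | 0.053 |
| 26 | 13 | 0.019 | 0.054 |

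**5. Why the independence formula does not apply.** 1 − 0.975^14 = 0.298. This overstates the risk, because the 14 tests are seven complementary splits of the same subjects and each exact test is conservative. Simulation is needed.

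**6. Simulation.** 20,000 trials per scenario. Every subject has the same true rate, the seven factors are independent, and each level is tested at its own exact critical value. The documents give no subgroup sizes, so the splits are assumptions. Probability of at least one significant subgroup at the 2.5% level:

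| N | Split | True 29% | True 33% |
|---|---|---|---|
| 52 | prevalences 30% to 75% | 0.12 | 0.26 |
| 52 | 50/50 | 0.139 | 0.298 |
| 52 | 70/30 | 0.138 | 0.288 |
| 52 | 80/20 | 0.094 | 0.219 |
| 47 | 50/50 | 0.143 | 0.301 |
| 47 | 70/30 | 0.083 | 0.187 |
| 47 | 80/20 | 0.142 | 0.258 |

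The single overall test rejects in about 1.5% of trials at 29% and about 6% at 33%. At 29% the ratio is roughly 0.12 / 0.015 = 8. In the first scenario at a true 33%, about 20% of trials have a significant subgroup while the overall test at the same level fails.

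**7. Effect of prognosis.** The runs in step 6 contain no prognostic effect. With one to three prognostic factors and assumed odds ratios of 2 to 3 (N = 52, 2.5% level), the figure is 14% to 24% at an overall rate of 29%, and 32% to 46% at 33%.

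**8. Timing.** From the end of March 2018 to 10 July 2018 is 30 + 31 + 30 + 10 = 101 days, just over three months.

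**The case against.** Several points on the other side stand.

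- A reader might infer that a significant subgroup is likely by chance. The figures do not support that. Under the 29% null it is about 12%. The independence formula at one-sided 5%, 1 − 0.95^14 = 0.51, uses a level that section 7.2.4.5 does not give to subgroups and ignores the overlap between them.
- At a true 33% the stated null is false, so those rejections are not type I errors. They show how easily the test is passed with no benefit from TAS-102, which partly reflects the choice of 29%.
- A reader might infer that the factors and the 600-day cut were chosen after results had been seen. The documents do not show this. They give planned dates only and no date for data fixation or the initial analysis, and both documents require the SAP to be finalized before data fixation.
- The additions are disclosed: the v4.0 revision history lists both parts of section 7.2.4.3 as new.
- The landmark analyses refer only to section 7.2.4.2, which is Kaplan-Meier estimation with confidence intervals. No test is specified there. The logistic model for the PFS rate already compares levels with mutual adjustment.
- The binomial test is headed as the main analysis, and no subgroup result is made a criterion of success.

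It might also be said that only the rate and its interval were meant to carry over to subgroups. The text does not say so. A dated entry in a revision history also does not tell a reader that the results are exploratory. A label alone would leave in place a test whose null does not suit a subgroup.

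**Conclusion.** The concern holds as a materially inflated error rate combined with an unsuitable null. It does not show that a false subgroup claim is probable. As written, the plan tests 14 subgroups against 29%. At the applicable 2.5% upper-tail level, at least one is significant in about 12% of trials at a true 29% (8% to 14%) and about 26% at 33% (19% to 30%). These figures rest on assumed subgroup sizes, independent factors and 47 to 52 subjects. They would be higher if the factors are prognostic, but by how much depends on odds ratios that the documents do not give. That a fixed 29% cannot separate treatment effect from prognosis needs no simulation.

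On timing, the supported statement is that six of the seven factors, the landmark analyses and the multivariable models are late additions in an open-label trial. Whether data had been seen is not known.

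**What to change.** In SAP section 7.2.4.3:
- State that the binomial test against 29% is not performed in subgroups.
- Report each level's PFS rate with an exact confidence interval, and the between-level difference with its interval. State that subgroup intervals are not interpreted against 29%. This is needed because a two-sided 95% exact lower limit above 29% is the same inference as one-sided p < 0.025.
- Identify the items added in v4.0 (six factors including the 600-day cut, the landmark analyses, the multivariable models) as late, exploratory additions.

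In section 7.2.4.5, state that the full-analysis-set test of the PFS rate is the only confirmatory test.

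The cost is SAP wording and fewer p-values; no new data are needed. The downside is that subgroup findings can be claimed only as exploratory.
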